9.7.2.4.1. Patients with venous thromboembolism risk factors

To describe changes in the utilisation of tofacitinib, this analysis will be stratified by the VTE reporting periods 1, 2 and 3.

The proportion of patients with one or more risk factors for VTE, identified prior to tofacitinib initiation, will be described and tabulated overall and by individual VTE risk factor (e.g., prior VTE and recent MI).

Logistic regression analyses will be used to calculate odds ratios along with their corresponding 95% confidence intervals and p values to formally compare the proportion of patients with VTE risk factors across VTE reporting periods 1, 2 and 3.

To enhance statistical power in detecting changes, a composite score for the VTE risk factors will also be generated by summing the individual VTE risk factors. Linear regression analyses will be employed to compare the VTE composite score across the VTE reporting periods. In addition to the summed composite score, the same analysis using a composite score weighting the risk factors may be considered in an exploratory fashion (weights will be developed and described in the SAP). Regression coefficients with their 95% confidence intervals and p values will be generated.

The proportion of patients diagnosed with UC, one or more VTE risk factors identified prior to tofacitinib initiation and no use of alternative therapy (i.e., biologic) prior to tofacitinib initiation whose ADD in Week 17 through Week 24, Week 25 through Week 32, Week 33 through Week 40 or Week 41 through Week 48 was >10 mg will be described and tabulated.

The proportion of patients who discontinue or continue to facitinib after developing one or more VTE risk factors while taking to facitinib will be described separately.

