urine) laboratory	Screening	for a creatinine (serum or urine) laboratory test.
testing		
TB screening	Outcome:	Defined as ≥1 procedure code or ≥1 ICD-10 diagnosis code
•	Screening	for TB (active and latent) screening.
	Outcome:	
	Monitoring	
Viral hepatitis B and C	Outcome:	Defined as ≥1 procedure code or ≥1 ICD-10 diagnosis code
screening	Screening	for viral hepatitis B and C screening.
-	Outcome:	
	Monitoring	
Absolute lymphocyte	Outcome:	Defined as ≥1 procedure code or ≥1 ICD-10 diagnosis code
count (ALC)	Screening	for ALC laboratory testing.
laboratory testing	Outcome:	
	Monitoring	
Absolute neutrophil	Outcome:	Defined as ≥1 procedure code or ≥1 ICD-10 diagnosis code
count (ANC)	Screening	for ANC laboratory testing.
laboratory testing	Outcome:	
	Monitoring	
Haemoglobin	Outcome:	Defined as ≥1 procedure code or ≥1 ICD-10 diagnosis code
laboratory testing	Screening	for haemoglobin laboratory testing.
	Outcome:	
	Monitoring	
Alanine	Outcome:	Defined as ≥1 procedure code or ≥1 ICD-10 diagnosis code
aminotransferase	Screening	for ALT and/or AST laboratory testing.
(ALT) and/or	Outcome:	
Aspartate	Monitoring	
aminotransferase		
(AST) laboratory		
testing		

Table 3. Operational definitions of study variables in Système National des Données de Santé

Variable	Role	Operational definition
Lipid panel (i.e., total	Outcome:	Defined as ≥1 procedure code or ≥1 ICD-10 diagnosis code
cholesterol, high-	Monitoring	for lipid panel laboratory testing.
density lipoprotein		
(HDL), low-density		
lipoprotein (LDL) and		
triglycerides (TG))		
laboratory testing		
Describe prescribing p	atterns over time: De	scribe changes in the utilisation of tofacitinib following the
		or use after the 2019 Article 20 referral, the 2021 signal
evaluation procedure,	and the 2022/2023 JA	Ki Article 20 referral
Adherence to recomme	endations for limitation	ons of use in patients with VTE risk factors (will be
stratified by VTE repo	rting period 1, 2, 3)	
Assessment of VTE risk	factors prior to initiati	on of tofacitinib
Prior VTE	Outcome: changes	Defined as ≥1 ICD-10 diagnosis code for VTE in the 12
	in use in patients	months prior to the index tofacitinib dispensing.
	with VTE risk	List of VTE codes in ANNEX 12. LIST OF DIAGNOSIS
	factors	CODES FOR VTE.
History of surgery,	Outcome: changes	Defined as ≥1 procedure code for a major surgery in the
major	in use in patients	3 months prior to the index tofacitinib dispensing.
	with VTE risk	
	factors	

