Heart failure	Outcome: changes in use in patients with VTE risk factors	Defined as ≥1 ICD-10 diagnosis code for heart failure while receiving tofacitinib therapy.
Use of combined hormonal contraceptives or hormonal replacement therapy	Outcome: changes in use in patients with VTE risk factors	Defined as ≥1 prescription dispensing of a combined hormonal contraceptives and/or hormonal replacement therapy (as identified by ATC codes) while receiving tofacitinib therapy.
Inherited coagulation disorder	Outcome: changes in use in patients with VTE risk factors	Defined as ≥1 ICD-10 diagnosis code for inherited coagulation disorder while receiving tofacitinib therapy.
Malignancy (non- metastatic and metastatic, excluding NMSC)	Outcome: changes in use in patients with VTE risk factors	Defined as ≥1 ICD-10 diagnosis code for malignancy (excluding NMSC) while receiving tofacitinib therapy.
Age ≥ 65 years	Outcome: changes in use in patients with VTE risk factors	Defined as age ≥65 years while receiving to facitinib.
Diabetes	Outcome: changes in use in patients with VTE risk factors	Defined as ≥1 ICD-10 diagnosis code for diabetes or ≥3 (or at least 2 in case of large pack sizes) prescription dispensing of oral antidiabetic agents and/or insulin (identified by ATC codes) while receiving tofacitinib therapy.
Hypertension	Outcome: changes in use in patients with VTE risk factors	Defined as ≥1 ICD-10 diagnosis code for hypertension or ≥3 (or at least 2 in case of large pack sizes) prescription dispensing of antihypertensive agents (identified by ATC codes) while receiving tofacitinib therapy.
Discontinuation of tofacitinib after developing ≥1 VTE risk factors while taking tofacitinib	Outcome: changes in use in patients with VTE risk factors	Defined as ≥1 VTE risk factor(s) while receiving tofacitinib therapy (as listed and defined above) plus 0 prescription dispensing for tofacitinib within a specific time window after the code for the first VTE risk factor.
g		Note: The time window for when to look for a tofacitinib prescription dispensing will be specific to the VTE risk factor(s) acquired while receiving tofacitinib therapy and will be operationalised during SAP development.
		Duration of tofacitinib therapy defined in Section 9.3.2.

Table 3. Operational definitions of study variables in Système National des Données de Santé

Variable Role Operational definition	
Discontinuation of Outcome: changes The same definition as above but of	only limited to VTE risk

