9.3.2. Duration of tofacitinib therapy

Duration of tofacitinib therapy will be defined as the time from the date of the index tofacitinib dispensing to the date of discontinuation of tofacitinib. The operational definitions for duration of tofacitinib therapy will be further elaborated in the SAP. For example, the following proxy may be used to estimate duration, that is, time between 2 prescription dispensing of tofacitinib, allowing for a grace period of a pre-determined length (e.g., 90 days) before being considered to have discontinued tofacitinib. The length of the grace period will be determined during development of the SAP.

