9.7.2.4.3. Patients with cardiovascular risk factors

To describe changes in the utilisation of tofacitinib, this analysis will be stratified by the CV and malignancy reporting periods 1, 2 and 3. The proportion of patients with one or more CV risk factors, identified prior to tofacitinib initiation, will be described and tabulated overall and for each individual CV risk factor.

Logistic regression analyses will be used to calculate odds ratios along with their corresponding 95% confidence intervals and p values to formally compare the proportion of patients with CV risk factors across CV and malignancy reporting periods 1, 2 and 3.

To enhance statistical power in detecting changes, a composite score for the CV risk factors will also be generated by summing the individual CV risk factors. Linear regression analyses will be employed to compare the CV composite score across the CV and malignancy reporting periods. In addition to the summed composite score, the same analysis using a composite score weighting the risk factors may be performed in an exploratory fashion (weights will be developed and described in the SAP). Regression coefficients with their 95% confidence intervals and p values will be generated.

Proportions will be stratified by sex, age (≥65 years versus < 65 years) and prior use of alternative therapy (e.g., biologic), pending sufficient sample size.

The proportion of patients who discontinue or continue to facitinib after developing one or more CV risk factors while taking to facitinib will be described separately. The proportion will be further stratified by sex, age (≥65 years versus < 65 years) and prior use of alternative therapy (e.g., biologic), pending sufficient sample size.

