9.7.2.4.4. Patients with malignancy risk factors

To describe changes in the utilisation of tofacitinib, this analysis will be stratified by the CV and malignancy reporting periods 1, 2 and 3. The proportion of patients with one or more malignancy risk factors, identified prior to tofacitinib initiation, will be described and tabulated overall and for each individual malignancy risk factor.

Logistic regression analyses will be used to calculate odds ratios along with their corresponding 95% confidence intervals and p values to formally compare the proportion of patients with malignancy risk factors across CV and malignancy reporting period 1, 2 and 3.

To enhance statistical power in detecting changes, a composite score for the malignancy risk factors will also be generated by summing the individual malignancy risk factors. Linear regression analyses will be employed to compare the malignancy composite score across the CV and malignancy reporting periods. In addition to the summed composite score, the same analysis using a composite score weighting the risk factors may be performed in an exploratory fashion (weights will be developed and described in the SAP). Regression coefficients with their 95% confidence intervals and p values will be generated.

Proportions may be stratified by age (≥65 years versus < 65 years) and prior use of alternative therapy (e.g., biologic), pending sufficient sample size.

The proportion of patients who discontinue or continue to facitinib after developing one or more malignancy risk factors while taking to facitinib will be described separately. Proportions will be stratified by age (≥65 years versus < 65 years) and prior use of alternative therapy (e.g., biologic), pending sufficient sample size.

9.7.2.5. Describe prescribing patterns over time: Describe changes in the utilisation of tofacitinib following the updated recommendations and limitations for use implemented after the JAKi 2022/2023 Article 20 referral

9.7.2.5.1. UC maintenance treatment dosage for patients with CV and malignancy risks, in addition to VTE risk factors

To describe changes in the utilisation of tofacitinib, this analysis will be stratified by the JAKi reporting periods 1, 2 and 3. The proportion of UC patients with CV or malignancy risk factors who have an ADD of > 10 mg in Weeks 17-24, Weeks 25-32, Weeks 33-40 and/or Weeks 41-48 of follow-up will be described and tabulated over each of the JAKi reporting periods.

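### Stopping after a new VTE, CV or malignancy risk factor is all-cause discontinuation reported under an adherence heading, with no same-window background rate planned

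*Protocol*

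**What the plan says.** Table 3 (section 9.3.1) defines discontinuation after a new VTE risk factor as at least one such factor arising on treatment, "plus 0 prescription dispensing for tofacitinib within a specific time window after the code for the first VTE risk factor". Continuation is the complement: at least one dispensing in the window. The CV and malignancy outcomes are built the same way. The window depends on the factor and "will be operationalised during SAP development". All three pairs sit in Table 3 blocks headed as adherence to limitations of use, while their role label is changes in use.

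Sections 9.7.2.4.1, 9.7.2.4.3 and 9.7.2.4.4 stratify by the relevant reporting periods 1, 2 and 3. They then say only that the proportions will be reported: "after developing one or more VTE risk factors while taking to facitinib will be described separately" for VTE, "after developing one or more CV risk factors while taking to facitinib will be described separately" for CV and "after developing one or more malignancy risk factors while taking to facitinib will be described separately" for malignancy. None of them names a rate in patients without a new factor. Section 9.7.2.1 tabulates overall duration of therapy by indication group and age, but not over a window matched to the risk factor.

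**The concern.** Patients leave a drug in the first year for many reasons, and the definition does not separate them. The proportion reported therefore mixes prescribers reacting to a new risk factor with stopping that would have happened anyway. Under an adherence heading, a reader may take the whole proportion as adherence.

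This matters because section 7 says data from this study, the companion utilisation study and the prescriber survey will together be used to judge whether the risk minimisation materials work. Section 9.9 does not mention the problem. Its discussion of adherence proxies (9.9.1.1, on suitable alternatives) covers only an error in the opposite direction, where non-adherence is overstated. Counting unrelated stops would make the materials look better than they are.

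A second difficulty concerns what adherence means here. Section 7 reports a recommendation to discontinue for suspected VTE and, separately, caution in patients with VTE risk factors. Table 3 pools a VTE event and the other factors in one discontinuation outcome under one heading. These places need to be reconciled with each other.

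**Working it through.** The protocol gives no stopping rate, window length or target for these outcomes, so there is no figure of its own to reproduce.

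**Inputs**
- Year length: 360 days (Table 3).
- Window: not given. 90 days is used because section 9.3.2 offers it as an example grace period; 180 days is shown as well.
- 12-month stopping d: not given. Assumed 30-50%, with 20-60% as a wider range, at a constant rate.
- Periods follow index date, and follow-up is 12 months from index (9.2.3 to 9.2.5).
- Period 1 for VTE: 17 months, to 31 May 2019. Period 1 for CV/malignancy: 42 months, to 30 June 2021.
- UC patients are eligible from May 2019 (9.2.2). That leaves 1 month of VTE period 1 and 26 months of CV/malignancy period 1.

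**1. Level within a period, with no reaction to the factor**

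Background share in w days: b = 1 − (1 − d)^(w/360).

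| d | 90 days | 180 days |
|---|---|---|
| 20% | 5.4% | 10.6% |
| 30% | 8.5% | 16.3% |
| 50% | 15.9% | 29.3% |
| 60% | 20.5% | 36.8% |

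For example, 1 − 0.70^0.25 = 0.085 and 1 − 0.50^0.25 = 0.159.

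**2. Change between periods, constant background**

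Observed stopping = 1 − (1 − b)(1 − r), where r is the true response.
- b = 8.5% and r = 0 in both periods: 8.5% against 8.5%, difference 0.
- r rising from 0 to 10%: 1 − 0.915 × 0.90 = 17.6%, a rise of about 9.2 points.

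A constant background therefore cancels when response does not change, and it only slightly dilutes a real change.

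**3. Change between periods, drifting background, r = 0**

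If d moves from 30% to 50%, the 90-day share moves from 8.5% to 15.9%. That is a spurious rise of 7.4 points. A move from 30% to 40% gives 8.5% to 12.0%, or 3.5 points.

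**4. How clean period 1 is as a baseline**

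Assume uniform initiation and full 12-month follow-up. Only patients who index in the last 12 months of the period have follow-up beyond its end, on average 6 of their 12 months. The share of follow-up time past the end is (12/L) × 0.5 for an eligible length L of at least 12 months.
- VTE, RA: (12/17) × 0.5 = 35%.
- VTE, UC (L = 1 month): mean time past the end is 11.5 of 12 months, or 96%.
- CV/malignancy, RA: (12/42) × 0.5 = 14%.
- CV/malignancy, UC: (12/26) × 0.5 = 23%.

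**The case against.** The best defence is that a comparator already exists. All three analysis sections stratify by reporting period, the objective is change over time, and section 9.5 describes period 1 as the baseline (though it says so for the proportions of initiators with risk factors). Step 2 shows that a constant background then cancels. This stands, and it rules out the reading that the plan has nothing to compare these proportions with. The defence does not cover the level within a period or drift (steps 1 and 3), and for VTE the baseline is itself contaminated (step 4). That last weakness should not be carried over in full to CV and malignancy, where the overlap is much smaller.

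A reader might also infer that the plan treats each stop as a response to the recommendation. No passage says so. The role label is changes in use, the proportions are only described, and no regression is named for them. The primary comparison in 9.5 concerns initiators. What remains is the adherence heading without a caveat.

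It is tempting to add that stopping around major surgery for failed UC treatment would be counted as adherence. That is conjecture: the protocol gives no procedure list for major surgery, and the factor must arise while on treatment.

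The window is properly left to the SAP and is not criticised. A reference group is different, because the analysis sections define the outcome without one and do not defer it.

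Finally, patients with a new event are sicker and more often in hospital, and not all inpatient drugs are captured (9.9.1.1, 9.9.2). A comparison with unaffected patients therefore does not isolate prescriber response. This also stands, and it limits what the remedy can claim.

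**Conclusion.** The concern holds in a limited form. These outcomes measure all-cause discontinuation. Within a reporting period, the proportion cannot be read as response to the recommendation, because no background rate over the same window is planned. On the assumed 30-50% annual stopping, 8.5-15.9% at 90 days would appear with no response at all (5.4-20.5% for 20-60%). Between periods, the stratification deals with a constant background but not with drift, where a move from 30% to 50% would add 7.4 points.

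Period 1 is a poor baseline for VTE, especially in UC, and a better one for CV and malignancy. The stopping rates, constant hazard and windows are assumptions, and the overlap shares rest on uniform initiation and full follow-up. The conclusion that level and background cannot be separated does not depend on the exact values. The change is worth making, but the primary comparison is not affected.

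**What to change.** For each of the VTE, CV and malignancy outcomes:

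1. For each patient with a new factor, take patients of the same indication group and reporting period who are still treated at the same time since index and have no new factor. Apply the same window, including any factor-specific length set in the SAP.
2. Report both stopping proportions and their difference with a 95% CI, by indication group and reporting period.
3. Label the proportions as all-cause discontinuation and continuation.
4. State in section 9.9 that the difference is a background benchmark and may still reflect illness severity or hospitalisation.
5. Reconcile the section 7 statements on suspected VTE and on VTE risk factors with the pooled outcome and its adherence heading in Table 3.

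The cost is modest programming on data already held, plus a few sentences of text. No new extraction is needed.

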9.7.2.4.2. Patients aged 65 years and older

To describe changes in the utilisation of tofacitinib among patients aged 65 years and older, analyses will be stratified by the VTE reporting periods 1, 2 and 3 and CV and malignancy reporting periods 1, 2 and 3. The following outcomes will be described:

- The proportion of patients aged 65 years and older initiating to facitinib on the index date without prior alternative therapies (defined as ≥1 biologic in the 12 months prior to index date) will be described and tabulated.
- The proportion of patients who discontinue to facitinib after turning 65 years old while receiving to facitinib will be described and tabulated.

• The proportion of patients who continue to facitinib after turning 65 years old while receiving to facitinib, overall and stratified by the use of alternative therapies prior to index to facitinib prescription dispensing, will be described and tabulated.

Logistic regression will be used to assess whether the distributions of these outcome variables are statistically significantly different across reporting periods.

9.7.2.4.3. Patients with cardiovascular risk factors

To describe changes in the utilisation of tofacitinib, this analysis will be stratified by the CV and malignancy reporting periods 1, 2 and 3. The proportion of patients with one or more CV risk factors, identified prior to tofacitinib initiation, will be described and tabulated overall and for each individual CV risk factor.

Logistic regression analyses will be used to calculate odds ratios along with their corresponding 95% confidence intervals and p values to formally compare the proportion of patients with CV risk factors across CV and malignancy reporting periods 1, 2 and 3.

To enhance statistical power in detecting changes, a composite score for the CV risk factors will also be generated by summing the individual CV risk factors. Linear regression analyses will be employed to compare the CV composite score across the CV and malignancy reporting periods. In addition to the summed composite score, the same analysis using a composite score weighting the risk factors may be performed in an exploratory fashion (weights will be developed and described in the SAP). Regression coefficients with their 95% confidence intervals and p values will be generated.

Proportions will be stratified by sex, age (≥65 years versus < 65 years) and prior use of alternative therapy (e.g., biologic), pending sufficient sample size.

The proportion of patients who discontinue or continue to facitinib after developing one or more CV risk factors while taking to facitinib will be described separately. The proportion will be further stratified by sex, age (≥65 years versus < 65 years) and prior use of alternative therapy (e.g., biologic), pending sufficient sample size.

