Variables: Demographic characteristics (age and sex), diagnoses (indication [including off-label use]), comorbidities, contraindicated use, VTE risk factors, CV risk factors and malignancy risk factors), use of alternative therapy (i.e., biologics) prior to initiation of tofacitinib, prior and current medications, procedures (including screening and monitoring tests), ADD and duration of tofacitinib therapy will be examined to address the objectives.

Data source: The study population will be sourced from the French national health claims database, the Système National des Données de Santé (SNDS), which covers >99% (~65 million insures) of the French population from birth or immigration to death or emigration.

Study size: 480 to 1,062 patients per indication group (e.g., RA/PsA and UC) are needed to detect a minimum meaningful difference with 80% statistical power and a two-sided 5% significance level in the proportion of tofacitinib initiators with risk factors of interest across different reporting periods. In contrast, 240 to 426 patients per indication group are needed to detect a minimum meaningful difference with 80% statistical power and a two-sided 5% significance level in the composite risk factor scores. Based on preliminary assessment of data from the SNDS database, it is anticipated that approximately 8,000 RA or PsA and 2,000 UC patients who initiate tofacitinib will be captured through the end of the indexing period (e.g., December 2024).

Data analysis: The analysis will be conducted separately by indication of tofacitinib ("RA or PsA" and "UC," unless otherwise specified). Results will be provided as descriptive statistics such as count and proportion of patients having taken the recommended laboratory tests prior to initiating tofacitinib. Utilisation of tofacitinib in patients with VTE risk factors, patients 65 years and older, patients with CV risk factors and patients with malignancy risk factors will be stratified by reporting periods (VTE, CV and malignancy, and the JAKi reporting periods) in accordance with the distribution of the revised aRMM materials following the 2019 Article 20 referral, the 2021 signal procedure, and the 2022/2023 JAKi Article 20 referral to contextualise the changes in patterns of use. Comparative statistical analyses will be conducted to describe changes in the use of tofacitinib across reporting periods.

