Study A3921321 is an ongoing DUS (i.e., component 2 described above) using secondary data from Sweden, Hungary, Germany and the Netherlands. This protocol (A3921403) describes another drug utilisation study in France that will complement Study A3921321. Data from the 2 DUS studies, together with the findings from the tofacitinib prescriber survey (A3921334), will be used to assess whether the aRMM materials are effective or not. This non-interventional study is designated as a post-authorisation safety study and is conducted by the MAH as a Category 3 commitment to the EMA.

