9.5. Study size

Comparative analyses for the changes in the proportions of patients with risk factors

For the comparative analyses, the study will assess changes in the proportion of tofacitinib initiators with risk factors of interest (e.g., VTE, elderly, CV, and malignancy) over different reporting periods (Section 9.2.4-9.2.6). The primary comparison of interest will be the proportion of tofacitinib initiators with risk factors during reporting period 3 (when full implementation of the updated aRMMs is expected) against that during reporting period 1 (baseline before implementation or notification of updated aRMMs). Secondary comparisons

b Data are updated once a year, usually by the end of August

of interest will be between reporting period 1 and reporting period 2, as well as reporting period 2 and reporting period 3 to assess any intermediate changes.

Sample size required for evaluating changes in the proportion of patients with risk factors across reporting periods was calculated using the following formula based on two independent sample *z*-test for proportions:⁸

$$N= \frac{(z_{\alpha/2}+z_{\beta})^2(p_1(1-p_1)+p_2(1-p_2))}{\epsilon^2}$$

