Based on these estimated numbers of patients during the entire study period and sample size calculation, the study is anticipated to have sufficient sample size to detect meaningful differences in the use of tofacitinib among patients with risk factors between the pre- and post-implementation period of updated aRMMs. All eligible patients during the study period will be included in the analysis. The number of patients will be actively monitored during the course of the study and the MAH will provide timely notification to the EMA if sufficient sample size is not reached during the planned study period.

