9.7. Data analysis

Descriptive statistics will be provided for all results. Categorical variables will be reported using frequency distributions. Ordinal variables will be reported using frequency distributions, means, standard deviations (SDs), minimums, 25th percentiles, medians, 75th percentiles and maximums, unless otherwise specified. Continuous variables will be reported

using means, SDs, minimums, 25th percentiles, medians, 75th percentiles and maximums, unless otherwise specified. When relevant, 95% CIs will be calculated for the study outcomes outlined in Section 9.3.1 (Outcomes) and Table 3. All analyses will be stratified by the approved indication or indication groups ("RA or PsA" and "UC"), unless otherwise specified. In addition, for the objective of "Describe prescribing patterns over time", comparative statistical analyses will be conducted to describe changes in the use of tofacitinib across reporting periods to assess the statistical significance of reductions in the use of tofacitinib among patients with risk factors (see below for further details). P-value < 0.05 indicates statistical significance.

Missing values will be reported as missing and no imputation will be undertaken. Results will be summarised in tables and figures in Microsoft® Excel and/or Word format.

Detailed methodology for summary and statistical analyses of data collected in this study will be documented in a SAP, which will be dated, filed and maintained by the sponsor. The SAP may modify the plans outlined in the protocol; any major modifications of primary endpoint definitions or their analyses would be reflected in a protocol amendment.

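### The Period 3 versus Period 1 regressions cannot separate a change following an aRMM update from a trend already under way, and the protocol neither plans a calendar-time analysis nor limits attribution.

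*Protocol*

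**What the plan says.** Section 9.5 fixes the main contrast: "The primary comparison of interest will be the proportion of tofacitinib initiators with risk factors during reporting period 3", set against reporting period 1. Section 9.7 gives the purpose of the tests as "to assess the statistical significance of reductions in the use of tofacitinib among patients with risk factors" and the criterion as "P-value < 0.05 indicates statistical significance". For cardiovascular risk factors, Section 9.7.2.4.3 says "Logistic regression analyses will be used to calculate odds ratios along with their corresponding 95% confidence intervals and p values to formally compare" the share of initiators who have them across the three reporting periods, with linear regression for the composite score. Sections 9.7.2.4.1, 9.7.2.4.2 and 9.7.2.4.4 follow the same pattern (regression across periods), and Section 9.7.2.5.1 compares UC maintenance dosing across the JAKi periods in the same way. None of them names a calendar-time term, a segmented model or covariate adjustment. Some proportions are to be stratified by sex, age or prior biologic use if numbers allow.

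Section 9.5 expects enough patients to detect meaningful "differences in the use of tofacitinib among patients with risk factors between the pre- and post-implementation period of updated aRMMs". Section 7 says that the data from this study, the sister drug utilisation study and the prescriber survey "will be used to assess whether the aRMM materials are effective or not".

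Annex 2 sets confounding aside because the study is descriptive and has no control groups. It marks analytic control of confounding as not applicable and comments that the study contains no measures of association. Section 9.9 does not mention secular trend.

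**The concern.** A model with period as its only term has as its null that the average over Period 1 equals the average over Period 3. For the cardiovascular set these are 42 and 26 months long, with midpoints 50 months apart (month 21 and month 71). Any steady movement in the mix of initiators enters the odds ratio in full, and a trend visible inside Period 1 is not used.

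The documents give reasons to expect movement. PsA patients can enter the pooled RA/PsA group only from May 2019, after 16 of the 17 months of VTE Period 1 (Table 2, Sections 9.2.2 and 9.2.4). The 2020 restriction for patients aged 65 and over falls inside cardiovascular Period 1, while age 65 or over is itself a cardiovascular and malignancy risk factor in Table 3.

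Two errors are possible. A trend that predates the aRMM update may be read as its effect, or an opposing trend, such as an ageing treated population, may hide a real fall of the size that Table 5 treats as meaningful.

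**Working it through.** **The plan's own figures.** Table 5 uses N = (z_α/2 + z_β)² [p1(1−p1) + p2(1−p2)] / ε², with (1.960 + 0.842)² = 7.849.
- 60% against 50%: 7.849 × (0.24 + 0.25) / 0.01 = 384.6, so 385.
- 70% against 55%: 7.849 × (0.21 + 0.2475) / 0.0225 = 159.6, so 160.

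All nine rows reproduce. The formula contains no time, which is why Section 9.5 can say that the required size does not depend on period length.

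**Inputs from the documents.** Period dates (9.2.4, 9.2.5); 4,000 RA/PsA and 1,000 UC initiators to December 2020, and 8,000 and 2,000 by December 2024 (9.5); UC entry from May 2019 (9.2.2); baseline proportion 30-80% (9.5); two-sided 5%.

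**Assumptions.** Even accrual before and after the end of 2020; the stated UC totals all eligible; linear drift, with its size not given in the protocol.

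**RA/PsA, cardiovascular periods.** Starts are 4,000/36 = 111.1 per month, then 4,000/48 = 83.3.
- n1 = 4,000 + 6 × 83.3 = 4,500; n3 = 26 × 83.3 = 2,167.
- Mean index time in Period 1 = (4,000 × 1.5 + 500 × 3.25)/4,500 = 1.69 years; in Period 3, 71/12 = 5.92 years; gap 4.22 years.
- Baseline 50%, drift 1 point/year: difference 4.22 points; SE = √(0.25/4,500 + 0.2482/2,167) = 1.30 points; ratio 3.24; chance of p < 0.05 = Φ(3.24 − 1.96) = 90%.
- Drift 0.5 point/year: 2.11/1.31 = 1.61, giving 36-37%.

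**UC, cardiovascular periods.** n1 = 1,000 + 6 × 20.8 = 1,125; n3 = 542; gap 3.63 years. At 1 point/year and 50%: 3.63/2.61 = 1.39, giving about 29%.

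Chance that drift alone is called significant, baselines 30% to 80%:

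| Drift (points/year) | RA/PsA, CV periods | RA/PsA, VTE periods | UC, CV periods |
|---|---|---|---|
| 0.1 | 6-7% | 6-7% | 5% |
| 0.25 | 13-17% | 12-16% | 6-7% |
| 0.5 | 37-50% | 33-46% | 11-14% |
| 1 | 90-97% | 86-96% | 29-38% |
| 2 | about 100% | about 100% | 80-90% |

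In VTE Period 1, UC contributes May 2019 alone, about 50 patients. There even 1 point/year gives only 8-9%.

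**Simulation check.** Simulating the RA/PsA cardiovascular contrast at baselines of 50-60% gave 34-39% at 0.5 point/year and 89-91% at 1 point/year. With a linear calendar-time term the two-sided rate was 3.5-6.0%.

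**Masking, RA/PsA, cardiovascular periods.** A true 10-point step fall with an upward drift of 2 points/year leaves −10 + 2 × 4.22 = −1.56 points. Then 1.56/1.31 = 1.19 and Φ(1.19 − 1.96) = 22%. Simulations gave 21-25% for the period-only model and 87-88% with the time term.

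**Price of the time term.** The standard error of the period effect rises about 2.0- to 2.5-fold for the VTE and cardiovascular periods. Without drift, power for a 10-point step (cardiovascular periods) is 88-90% in RA/PsA. In UC with May 2019 entry it is about 23-27%, against 97% for the period contrast.

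**Gradual uptake, no drift.** When a true 10-point RA/PsA fall is spread over cardiovascular Periods 2 and 3, a segmented model with steps only finds it in about 31% of runs. Spread over Period 3 alone, the figure is 8-9%. The period contrast finds 96-100%.

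**The case against.** The strongest reply is that Section 8 asks only for a description of changes following the updates. For that aim, a significant odds ratio under drift is correct, because the mix did change. The percentages above are errors only if the result is read causally. The protocol nowhere says that p < 0.05 shows that an aRMM worked, and effectiveness is judged jointly with another study and a survey. This stands as a reason to keep the period contrast. It does not remove the concern, because Sections 7 and 9.7 carry tests for reductions into an effectiveness judgement without any caution on attribution.

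A second reply is that model terms belong in the SAP. The protocol does not forbid a time term, and Section 9.7 lets the SAP modify the plan. That is fair, and a reader should not infer that calendar-time analysis is ruled out. But the protocol does take positions of its own: Annex 2 declares confounding control not applicable and denies measures of association although odds ratios are planned, and Section 9.9 omits secular trend. The checklist is dated November 2022, and Section 5 records the formal comparisons as added in October 2023, so those entries may simply be out of date.

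Two stronger readings are tempting. One is that any drift will be declared significant. The table shows otherwise: at 0.1 to 0.25 point/year rejection stays below 20% in RA/PsA, and in UC it is under 40% even at 1 point/year. The other is that a segmented step should replace the period contrast as the sole basis for attribution. Sections 9.2.4 to 9.2.6 allow for a period of distribution and uptake, and the gradual-uptake results show that such a rule would discard real effects. Nor does a linear term remove an abrupt shift such as PsA entry, although a plot would show it.

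**Conclusion.** The concern holds in a limited form. The planned contrasts describe change between periods but cannot attribute it to an aRMM update, and the protocol does not say so. In RA/PsA, at the projected volumes, drift of 0.5 to 1 point per year is enough to produce a significant reduction in about a third to nine-tenths of runs with no aRMM effect. Upward drift of 2 points per year hides a 10-point fall in about three-quarters or more of runs. In UC the false-positive risk is smaller, and a segmented model has too little power to settle the matter.

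These sizes depend on assumed linear drift and even accrual. The distortion is present under any drift, but a false significant result is not. The documents do not show that drift of this size exists, nor that the period contrast is wrong for its descriptive purpose.

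**What to change.** - Keep the Period 3 versus Period 1 contrast as the stated description of change.
- Beside it, prespecify (a) a plot of monthly or quarterly proportions by index date and (b) a supportive segmented model with linear calendar month of index and terms at the Period 2 and Period 3 starts. Allow a change in slope, so that gradual uptake is not absorbed by the common trend. Use the same structure for the composite scores.
- State that a significant period odds ratio alone will not be attributed to the aRMM, and that attribution will consider both analyses.
- Where the pre-period is short or numbers are small (VTE Period 1 for UC, and UC generally, with about 25% power for a 10-point step), report the contrast as descriptive only.
- Add secular trend to Section 9.9, and correct the Annex 2 entries on confounding and measures of association.

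The cost is one extra model and plot per outcome on data already held, plus wording. Intervals will be wide and often inconclusive, chiefly in UC. The power figures above are for a model without slope change, and adding those terms will widen the intervals further.
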